### 2.2.3 Clinical Safety Summary

Olaparib monotherapy has been associated with adverse reactions generally of mild or moderate severity (Common Terminology Criteria for Adverse Events v.5.0 [CTCAE] Grade 1 or 2) and generally not requiring treatment discontinuation (Investigator's Brochure, 2018). In a pool of 1248 patients, the most frequently observed adverse reactions across clinical trials in patients receiving olaparib monotherapy ( $\geq 10\%$ ) were nausea, vomiting, diarrhea, dyspepsia, fatigue, headache, dysgeusia, decreased appetite, dizziness, and anemia. Anemia and other hematologic toxicities were generally low grade (Grade 1 or 2). However, anemia was the most commonly reported Grade  $\geq 3$  adverse event (AE) reported in clinical trials. The median time to first report of anemia was approximately 4 weeks (approximately 7 weeks for Grade  $\geq 3$ ). Anemia can be managed with dose interruptions, dose reductions, and blood transfusions where appropriate. In one Phase 3 trial in ovarian cancer patients, the incidence of anemia was 43.6% of patients, with Grade  $\geq 3$  in 19.5% of patients, leading to dose interruptions (16.9%), dose reductions (8.2%), discontinuation of treatment (3.1%). In addition, 17.9% of patients treated with olaparib required one or more blood transfusions during treatment.

In clinical studies with olaparib the incidence of Grade  $\geq 2$  shifts (elevations) from baseline in blood creatinine was approximately 15% (Investigator's Brochure, 2018). Data from a double-blind placebo-controlled study showed median increase up to 23% from baseline remaining consistent over time and returning to baseline after treatment discontinuation, with no apparent clinical sequelae; 90% of patients had creatinine values of Grade 0 at baseline and 10% were Grade 1 at baseline.

Nausea was generally reported very early, with first onset within the first month of olaparib treatment in the majority of patients (Investigator's Brochure, 2018). Vomiting was reported early, with first onset within the first 2 months of olaparib treatment in the majority of patients. Both nausea and vomiting were reported to be intermittent for the majority of patients and can be managed by dose interruption, dose reduction and/or antiemetic therapy. Antiemetic prophylaxis was not required.

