- 3.1.11 Previous cytotoxic chemotherapy must have been completed at least 3 weeks and radiotherapy at least 2 weeks prior to Day 1 of treatment on the study, and all AEs (excluding alopecia) due to agents administered more than 4 weeks earlier should have recovered to  $<$  Grade 1. Patients with hematologic malignancies are expected to have hematologic abnormalities at study entry. Hematologic abnormalities that are thought to be primarily related to leukemia are not considered to be toxicities (AEs) and do not need to resolve to  $<$  Grade 1.
- 3.1.12 ECOG performance status 0-2 (Karnofsky  $\geq 60\%$ , see Appendix A).
- 3.1.13 Patient must have recovered from toxicities of any prior treatment regimen (no CTCAE grading over 1 for non-hematological toxicities, return to baseline for hematological values).
- 3.1.14 Ability to understand and the willingness to sign a written informed consent document. Patients with impaired decision-making capacity may have a close relative, guardian, caregiver, or Legally Authorized Representative consent on their behalf
- 3.1.15 Patients must have adequate organ function measured within 28 days prior to administration of study treatment as defined below:
- Total bilirubin  $\leq 1.5x$  institutional upper limit of normal (ULN) unless considered due to Gilbert's syndrome
  - Aspartate aminotransferase (AST) (Serum Glutamic Oxaloacetic Transaminase [SGOT]) / Alanine aminotransferase (ALT) (Serum Glutamic Pyruvate Transaminase [SGPT])  $\leq 2.5 x$  institutional upper limit of normal unless considered due to organ leukemic involvement. If liver metastases are present in which case they must be  $\leq 5x$  ULN
  - Creatinine clearance of  $> 30$  ml/min

- Patients are eligible for this study if low blood count and transfusion support are due to the MDS/AML.

3.1.16 Patients must have, in the best estimate of the treating physician, a life expectancy of at least 12-16 weeks.

3.1.17 Postmenopausal or evidence of non-childbearing status for women of childbearing potential: negative urine or serum pregnancy test within 28 days of study treatment and confirmed prior to treatment on Day 1.

Postmenopausal is defined as:

- Amenorrheic for 1 year or more following cessation of exogenous hormonal treatments
- Luteinizing hormone (LH) and Follicle stimulating hormone (FSH) levels in the post menopausal range for women under 50
- radiation-induced oophorectomy with last menses >1 year ago

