The safety and efficacy will be evaluated by an independent data review committee at each critical step of the protocol. Given the patient population, we considered a potential drop-out rate of 15%. Expected monthly accrual is 3-4 patients per month, with a proposed total sample size of 94 patients, over 2 years.

Demographic information such as age and race will be tabulated. Descriptive statistics, including means, standard deviations, and ranges for continuous parameters, as well as percentages and frequencies for categorical parameters, will be presented. Adverse medical events will be tabulated. CTCAE Grade 3 and Grade 4 laboratory abnormalities will be listed.

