## 9.4 Analysis of Secondary Endpoints

#### 9.4.1 Toxicity Evaluation and Reporting

All patients will be evaluated for toxicity.

- Non-hematologic toxicity will be evaluated by CTCAE v5 criteria.
- Hematologic toxicity will be defined using specific AML criteria: a hematologic dose limiting toxicity will be defined by the absence of the recovery of a cytopenia (ANC, PLT, Hgb) to baseline levels (Day 1 of the cycle) within 6 weeks of Day 1, in the absence of signs of active disease in blood and bone marrow.

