## 10.3 Expedited Adverse Event Reporting

### 10.3.1 Rave CTEP-AERS Integration

The Cancer Therapy Evaluation Program Adverse Event Reporting System (CTEP-AERS) integration enables evaluation of post-baseline AEs entered in Rave to determine whether they require expedited reporting, and facilitates entry in CTEP-AERS for those AEs requiring expedited reporting.

All AEs that occur after baseline are collected in Medidata Rave using the Adverse Event form, which is available for entry at each treatment or reporting period, and used to collect AEs that start during the period or persist from the previous reporting period. The Clinical Research Associate (CRA) will enter AEs that occur prior to the start of treatment on a baseline form that is not included in the Rave-CTEP-AERS integration. AEs that occur prior to enrollment must begin and end on the baseline Adverse Event form and should not be included on the standard Adverse Events form that is available at treatment unless there has been an increase in grade.

Prior to sending AEs through the rules evaluation process, site staff should verify the

following on the Adverse Event form in Rave:

- The reporting period (course/cycle) is correct, and
- AEs are recorded and complete (no missing fields) and the form is query-free (fields added to the form during study build do not need to be query-free for the integration call with CTEP-AERS to be a success).

The CRA reports AEs in Rave at the time the Investigator learns of the event. If the CRA modifies an AE, it must be re-submitted for rules evaluation.

Upon completion of AE entry in Medidata Rave, the CRA submits the AE for rules evaluation by completing the Expedited Reporting Evaluation form. Both NCI and protocol-specific reporting rules evaluate the AEs submitted for expedited reporting. A report is initiated in CTEP-AERS using information entered in Medidata Rave for AEs that meet reporting requirements. The CRA completes the report by accessing CTEP-AERS via a direct link on the Medidata Rave Expedited Reporting Evaluation form.

In the rare occurrence that Internet connectivity is lost, a 24-hour notification is to be made to CTEP by telephone at [contact]. Once Internet connectivity is restored, the 24-hour notification that was phoned in must be entered immediately into CTEP-AERS using the deep link from Medidata Rave.

Additional information about the CTEP-AERS integration is available on the CTSU website:

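### The only laboratory-specific safety output is a grade 3-4 listing with no stated baseline, so it cannot separate cytopenias present at entry from on-treatment worsening

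*Combined protocol and SAP*

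**What the plan says.** - **Laboratory output (9.1.1).** "CTCAE Grade 3 and Grade 4 laboratory abnormalities will be listed". No section plans a shift table, a change from baseline, a worst on-treatment grade or a definition of a treatment-emergent laboratory abnormality.
- **Adverse event output (9.1.1).** "Adverse medical events will be tabulated", with no lower grade limit.
- **Entry counts (3.1.11, 3.1.15).** "Patients with hematologic malignancies are expected to have hematologic abnormalities at study entry", and "Patients are eligible for this study if low blood count and transfusion support are due to the MDS/AML".
- **Adverse event form (10.3.1).** Events that began before enrollment stay on a baseline form. They "should not be included on the standard Adverse Events form that is available at treatment unless there has been an increase in grade".
- **Hematologic toxicity (9.4.1).** The dose-limiting event is failure of "recovery of a cytopenia (ANC, PLT, Hgb) to baseline levels (Day 1 of the cycle) within 6 weeks of Day 1", provided there is no active disease in blood and marrow.
- **Creatinine (2.2.3).** The incidence of grade 2 or higher "shifts (elevations) from baseline in blood creatinine was approximately 15" per cent. A placebo-controlled study showed a median rise of as much as 23%, reversible on stopping.
- **Collection (section 11).** Blood counts and serum chemistry, including creatinine, are taken pre-study and in every cycle.

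**The concern.** Safety and tolerability is a secondary objective (1.2.5), and section 2.2.3 names anemia as the most common grade 3 or higher event with olaparib. In this population the disease itself lowers the same counts. A listing of absolute grades puts a patient who entered at grade 4 and stayed there beside one who fell from grade 1 to grade 4, with nothing stated to tell them apart.

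Creatinine has the opposite problem. The documents describe the effect as a movement from each patient's own starting value, while the planned output shows only values that reach grade 3. At stake is whether the report can say how many patients had new or worse abnormalities on olaparib.

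**Working it through.** The plan states no figure on this point, so there is none to reproduce. The check has four steps.

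**1. What the listing can show.** Take three patients with grade 4 neutrophils in cycle 2 whose pre-study grades were 4, 3 and 1. As section 9.1.1 is worded, all three give the same entry. The adverse event form would pick up the second and third as increases in grade. It shows nothing further for the first, because grade 4 is the highest laboratory grade short of death.

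**2. Whether other rules fill the gap.**

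| Section | Counts covered | Reference used | Who is covered |
|---|---|---|---|
| 7.2 | Grade 4 neutrophils or platelets beyond 42 days | None; interruption applies whatever the entry count | Limit: patients with a documented response. Interruption: no active disease |
| 9.1.3 | Grade 4 neutrophils or platelets, treatment not restarted within 42 days | No baseline value | No active disease |
| 9.4.1 | Neutrophils, platelets, hemoglobin not recovered in 6 weeks | Day 1 of the cycle | No active disease |
| 10.3.1 | Any recorded adverse event | Pre-enrollment grade | Recorded events only |

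The first three are decision rules for patients without active disease or with a response. At the design's own target rates (9.1.1), 1 − 0.50 = 50% of IDH-inhibitor-naive and 1 − 0.35 = 65% of exposed patients would not reach composite CR. Those with persisting disease fall outside these rules. Hemoglobin appears only in 9.4.1, where the reference is Day 1 of the cycle rather than the pre-study value, so change since entry is not measured. None of the four summarises counts for all treated patients.

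**3. Entry cytopenias (illustration).** The documents do not give the share q entering with a grade 3-4 count. Assuming q = 30%, 50% or 70% of the proposed 94 patients:

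- already at grade 3-4 at entry: 94q = 28.2, 47.0, 65.8
- below grade 3, and so able to have an emergent grade 3-4 count: 94(1 − q) = 65.8, 47.0, 28.2
- the same in the smallest arm (12 patients): 12(1 − q) = 8.4, 6.0, 3.6

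**4. Creatinine (illustration).** Applying the 15% from section 2.2.3:

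- 0.15 × 94 = 14.1 patients. The cohort totals in 9.1.1 add to 39 + 14 + 39 + 12 = 104, which gives 15.6.
- By cohort: 0.15 × 39 = 5.9 in each naive cohort, 0.15 × 14 = 2.1 and 0.15 × 12 = 1.8.

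The 15% is for grade 2 or higher and is not divided further. The number below grade 3, and so absent from the listing, lies anywhere from 0 to about 14 of 94.

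Calculated clearance deserves its own summary. Cockcroft-Gault clearance (the equation named in 7.5) is inversely proportional to creatinine. With age and weight unchanged, a patient with a full 23% rise has clearance multiplied by 1/1.23 = 0.81.

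**The case against.** The strongest reply is that the listing is not the whole safety evaluation. Section 9.4.1 judges cytopenia against a Day 1 value with disease inactive, the stopping rule also requires inactive disease, and the adverse event form filters out unchanged entry events. Adverse events are tabulated at every grade, increased creatinine is an expected term in the CAEPR (10.1), and section 10.4 requires all adverse events to be reported. Nothing in 9.1.1 forbids printing pre-study values beside the listed ones, and the general sentence on descriptive statistics might be read to include laboratory data.

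Much of this stands. A reader might infer that the plan confuses disease and drug effects throughout its safety reporting. The documents do not support that; the defect lies in the laboratory output. A reader might also infer that the known creatinine effect is confined to grades 1-2 and will be lost. Section 2.2.3 reports grade 2 or higher shifts without a split, and a recorded rise reaches the adverse event table. Nor do 6.1 and 7.5 attribute their renal dose thresholds to this shift: 7.5 applies whatever the cause, and 2.2.3 notes no evident clinical consequence.

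What the reply does not supply is a baseline-referenced summary for all treated patients, or a rule for when a laboratory change must be recorded as an adverse event. The descriptive-statistics sentence names no laboratory parameter, time point or comparison.

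It is also fair to say that a shift table separates old from new abnormalities, not olaparib from progression. That limits what the remedy can claim but does not remove the need for it.

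**Conclusion.** The point holds for the laboratory output and is minor. As written, the listing cannot separate counts already at grade 3-4 before treatment from on-treatment worsening, and it shows creatinine changes only from grade 3 up. The primary endpoint, sample size and stopping rule do not depend on it.

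The size cannot be fixed from the documents. The entry share q is an assumption, and the creatinine illustration carries the rate from section 2.2.3 into a different population. A reader may be tempted to turn the listing into an inflated toxicity rate and compare it with the 19.5% grade 3 or higher anemia in 2.2.3. The documents do not support that comparison. The 19.5% comes from an ovarian cancer trial and covers anemia alone, it would apply only to patients not already at grade 3-4, and the plan calls for a listing, not a rate.

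Separately, sections 7.2, 9.1.3 and 9.4.1 describe hematologic toxicity with different counts, references and disease conditions. They must be reconciled; no view is taken here on which is right.

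**What to change.** In 9.1.1, keep the listing as a supplement and add:

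- By-arm shift tables from pre-study grade to worst on-treatment grade, all grades, for neutrophils, platelets, hemoglobin and creatinine.
- Treatment-emergent grade 3-4 counted among patients below grade 3 at baseline, with that denominator printed.
- Patients at grade 3 or grade 4 at baseline shown separately, including any move from grade 3 to grade 4.
- Creatinine and calculated creatinine clearance summarised as change from baseline by cycle.
- A statement that the tables separate pre-existing from new or worsened abnormalities, and do not separate olaparib from disease progression.

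Also have the protocol team reconcile the references for hematologic toxicity in 7.2, 9.1.3 and 9.4.1.

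The cost is one paragraph and a few tables. Counts, chemistry and weight are already scheduled pre-study and in each cycle, so no new assessment is needed. The price is a smaller denominator for emergent rates, most visible in the two exposed arms, so those results should be given as counts.

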### 9.1.2 Primary Endpoints

The primary objective of this stratified Phase 2 study is to determine the CR using a modified CR endpoint (CR+CRi+CRh).

The safety and efficacy will be evaluated by an independent data review committee at each critical step of the protocol.

#### 9.1.2.1 Efficacy Evaluation

Clinical efficacy will be evaluated by MDS International Working Group (IWG) 2006 criteria (Cheson *et al.*, 2006) and AML IWG 2003 criteria (Cheson *et al.*, 2003) after 6 cycles of treatment. The primary endpoint will be cumulative composite CR (CR, CRi, CRh) and we will also record the cumulative ORR will include complete remission (CR), complete remission with incomplete blood count recovery (CRi), partial response (PR), and bone marrow complete remission (marrow CR/MLFS) achieved at least at one point during these 6 cycles.

### 9.1.3 Stopping Rule for Toxicity

Treatment and study participation may be stopped for excessive toxicity, defined as “any non-hematologic SAE at least possibly related to the drug leading to a treatment interruption of more than 2 weeks or any grade 4 ANC or PLT toxicity for which treatment can’t be restarted within 42 days of the initiation of the cycle and in the absence of active disease. Febrile neutropenias/neutropenic infections are excluded from this definition.”

The maximum toxicity rate allowed in the protocol will be 20% globally and 20% in each individual arm. We will have monthly evaluations of the toxicity rate during the study as well as for study milestones (end of stage 1 of the Simon design for each individual arm). Data will be reviewed by the coordinating team and the local PI. Based on the number of treated patient and the number of patients qualifying for an excessive toxicity, we will have a go/no-go decision for the continuation of the study and/or arm:

Number of patients	Hold inclusions if DLT are seen in
0-10	2 pts or more
11-15	3 pts or more
16-20	4 pts or more
21-25	5 pts or more
26-30	6 pts or more
31-35	7 pts or more

## 9.2 Sample Size/Accrual Rate

Expected monthly accrual is 3-4 patients per month, with a proposed total sample size of 94 patients, over 2 years.

Racial Categories	Ethnic Categories				Total
	Not Hispanic or Latino		Hispanic or Latino		
	Female	Male	Female	Male	
American Indian/ Alaska Native	1	1	1	1	4
Asian	2	2	0	0	4
Native Hawaiian or Other Pacific Islander	1	1	0	0	2
Black or African American	6	6	4	4	20
White	20	20	10	10	60
More Than One Race	2	0	2	0	4
Total	32	30	17	15	94

## 9.3 Stratification Factors

Patients will be stratified based on prior exposure to IDH inhibitors. Both untreated and pre-treated cohorts will be evaluated independently from the statistical perspective. AML and MDS patients will also be analyzed separately.

## 9.4 Analysis of Secondary Endpoints

#### 9.4.1 Toxicity Evaluation and Reporting

All patients will be evaluated for toxicity.

- Non-hematologic toxicity will be evaluated by CTCAE v5 criteria.
- Hematologic toxicity will be defined using specific AML criteria: a hematologic dose limiting toxicity will be defined by the absence of the recovery of a cytopenia (ANC, PLT, Hgb) to baseline levels (Day 1 of the cycle) within 6 weeks of Day 1, in the absence of signs of active disease in blood and bone marrow.

#### 9.4.2 Evaluation of Objective Response Rate

The effectiveness of the drug in patients for each cohort will be independently assessed by composite CR rate (CR+CRi+CRh). Objective Response Rate (ORR) will be included as a secondary endpoint, calculated as a composite CR+MLFS+PR. The exact two-sided 95% confidence intervals for the ORR will be reported. For lifetime data analyses, e.g., overall and progression free survival, the study survival will be estimated using the Kaplan-Meier method with the 95% confidence intervals (CIs). The CI based on the Greenwoods variance will be reported. In addition, the possible risk factors will be compared for survival with log-rank test. For multivariate analysis, the proportional hazards Cox model will be applied to investigate potential prognostic factors, such as age and stage of disease on the survival data. The adjusted p-values of the odds ratios and the adjusted 95% confidence interval will be reported.

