### **1.2 Secondary Objectives**

- 1.2.1 To determine the overall response rate (ORR) to olaparib using a composite ORR endpoint (CR + morphologic leukemia-free state [MLFS] + partial response [PR]) in patients with IDH mutant AML or MDS treated with olaparib.
- 1.2.2 To establish the progression free survival (PFS) of patients with IDH mutant AML or MDS treated with olaparib.
- 1.2.3 To determine the overall survival (OS) of patients with IDH mutant AML or MDS treated with olaparib.
- 1.2.4 To establish the duration of response (DOR) to treatment with olaparib.
- 1.2.5 To evaluate the safety and tolerability of olaparib in AML or MDS patients.

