### 9.6.2 Evaluation of Response

All patients that finish at least 1 cycle of therapy will be considered evaluable for clinical response. Clinical efficacy (Cumulative Overall Response Rate, ORR) will be evaluated by MDS IWG 2006 criteria (Cheson *et al.*, 2006) and AML IWG 2003 criteria (Cheson *et al.*, 2003) after 6 cycles of treatment. Cumulative ORR will include CR, Cri, PR, marrow CR achieved at least at one point during these 6 cycles.

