## 12. MEASUREMENT OF EFFECT

### 12.1 Antitumor Effect – Hematologic Tumors

For patients not previously exposed to IDH inhibitors, response is assessed after cycles 1, 3, 6, 9, and 12 for the first year. For patients *with* prior IDH inhibitor exposure, response is assessed after cycles 3, 6, 9, and 12 for the first year on treatment.

Category	Definition	Comment
Complete Response (CR)	Bone marrow blasts <5%; absence of circulating blasts and blasts with Auer rods; absence of extramedullary disease; ANC $\geq 1.0 \times 10^9/L$ (1,000/mcL); platelet count $\geq 100 \times 10^9/L$ (100,000/mcL)*	
CR with incomplete hematologic recovery (CRi)/CRh	All CR criteria except for residual neutropenia ( $<1.0 \times 10^9/L$ [1,000/mcL]) or thrombocytopenia ( $<100 \times 10^9/L$ [100,000/mcL])* CRh: complete remission with partial hematological recovery (platelets > 50,000 mcL and ANC > 500/mcL)	
Morphologic leukemia-free state (“marrow CR”, MLFS)	Bone marrow blasts <5%; absence of blasts with Auer rods; absence of extramedullary disease; no hematologic recovery required	Marrow should not merely be aplastic—at least 200 cells should be enumerated, or cellularity should be at least 10%
Partial response (PR)	All hematologic criteria of CR; decrease of bone marrow blast percentage to between 5% and 25%; and decrease of pretreatment bone marrow blast percentage by at least 50%	Especially important in the context of phase 1-2 clinical trials
Stable disease (SD)	Absence of CR, CRi, PR, MLFS; and criteria for PD not met	The period of stable disease should last at least 3 months

Category	Definition	Comment

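### ORR is defined in two incompatible ways, and the formula in sections 1.2.1 and 9.4.2 leaves out CRi and CRh, both of which count as primary-endpoint successes

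*Combined protocol and SAP*

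**What the plan says.** Four sections of the combined protocol and SAP define ORR.

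- Section 1.2, objective 1.2.1: "using a composite ORR endpoint (CR + morphologic leukemia-free state [MLFS] + partial response [PR". CRi and CRh are not named.
- Section 9.4.2: "Objective Response Rate (ORR) will be included as a secondary endpoint, calculated as a composite CR+MLFS+PR". This is the same formula. An exact two-sided 95% confidence interval is promised for it.
- Section 9.1.2.1: after CR, the list continues "complete remission with incomplete blood count recovery (CRi), partial response (PR), and bone marrow complete remission (marrow CR/MLFS". CRi is now included; CRh is not named.
- Section 9.6.2: "Cumulative ORR will include CR, Cri, PR, marrow CR achieved at least at one point during these 6 cycles". This has the same content as 9.1.2.1.

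The primary endpoint is stable throughout. Section 9.1.2 sets out "to determine the CR using a modified CR endpoint (CR+CRi+CRh", and 9.4.2 repeats it as "independently assessed by composite CR rate (CR+CRi+CRh" in the sentence just before its ORR formula.

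The response table in section 12.1 gives CR, CRi/CRh, MLFS and PR separate rows. It does not say whether the categories are mutually exclusive or nested.

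**The concern.** An overall response rate should contain every patient whom the complete-response endpoint counts as a success. Read literally, the formula in the objective and in the analysis section does not: two of the three primary-endpoint categories are missing. A programmer following 9.4.2 and one following 9.6.2 would report different secondary results from the same data, and the 9.4.2 version could come out below the primary rate. Such a figure is hard to interpret.

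The choice between formulas would also be open after the responses are known. Duration of response is exposed too: 9.4.3 starts the clock at the first documented response but does not say which categories qualify.

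**Working it through.** The plan states no ORR value, target or power, so there is no figure to reproduce. The check compares the definitions, applies simple algebra and then uses illustrative counts.

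**Step 1: the definitions side by side**

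| Category | Primary (9.1.2) | ORR in 1.2.1 and 9.4.2 | ORR in 9.1.2.1 and 9.6.2 |
|---|---|---|---|
| CR | yes | yes | yes |
| CRi | yes | no | yes |
| CRh | yes | no | not named (shares the CRi row in 12.1) |
| MLFS / marrow CR | no | yes | yes |
| PR | no | yes | yes |

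**Step 2: algebra, assuming one category per patient**

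ORR by 9.4.2 minus composite CR = (CR + MLFS + PR) − (CR + CRi + CRh) = (MLFS + PR) − (CRi + CRh).

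This is negative whenever CRi + CRh exceeds MLFS + PR. The gap between the two ORR formulas is the number of CRi patients, plus CRh if CRh is read as part of CRi.

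**Step 3: illustration**

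The inputs are N = 39 and 17 successes, the full size and efficacy boundary of each IDH-inhibitor-naïve arm in the 9.1.1 table. The split across categories is assumed. Composite CR is held at 17/39 = 43.6%, with 2 MLFS and 2 PR.

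| CRi + CRh | CR | ORR by 9.4.2 | ORR with CRi and CRh |
|---|---|---|---|
| 0 | 17 | (17+4)/39 = 53.8% | 21/39 = 53.8% |
| 4 | 13 | (13+4)/39 = 43.6% | 21/39 = 53.8% |
| 8 | 9 | (9+4)/39 = 33.3% | 21/39 = 53.8% |
| 12 | 5 | (5+4)/39 = 23.1% | 21/39 = 53.8% |

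The row with 8 CRi/CRh is the example in the summary: 33% against a composite CR of 44% and a full ORR of 54%.

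The intervals move as well. With one PR fewer (9 CR, 8 CRi/CRh, 2 MLFS, 1 PR), the 9.4.2 formula gives 12/39 = 30.8% (exact 95% CI 17.0 to 47.6%). The full formula gives 20/39 = 51.3% (34.8 to 67.6%).

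**Step 4: cases without inversion**

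- 9 CR, 8 CRi/CRh, 5 MLFS, 3 PR: the 9.4.2 formula gives (9+5+3)/39 = 43.6%, equal to composite CR. The full ORR is 25/39 = 64.1%.
- 9 CR, 8 CRi/CRh, 6 MLFS, 4 PR: the 9.4.2 formula gives (9+6+4)/39 = 48.7%, above composite CR. The full ORR is 27/39 = 69.2%.

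So the shortfall against the full formula persists even when ORR does not fall below composite CR.

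**Step 5: does this reach the primary analysis?**

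No. Exact calculation from the design table gives type I error 0.0455 and power 0.804 for the naïve arms, 0.0286 and 0.905 for exposed AML, and 0.0179 and 0.822 for exposed MDS. All meet the stated alpha and beta. They concern composite CR, and ORR does not enter.

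**The case against.** Two readings would remove the inversion, and both are plausible.

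First, plain CR in the ORR formula may be shorthand for the composite. Section 9.1.2 uses the bare term for its composite endpoint, 9.1.1 calls the null value a CR rate, and not repeating an expansion given one sentence earlier is ordinary drafting. The listing of CRi in 9.1.2.1 and 9.6.2 suggests that inclusion was intended. Against this, 9.4.2 writes the composite out and then uses plain CR in the next sentence, and 9.1.2.1 lists CR and CRi as separate components of ORR.

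Second, CRi and CRh patients may already count under MLFS. Section 12.1 defines CRi as "All CR criteria except for residual neutropenia" or thrombocytopenia, while MLFS requires no blood-count recovery. Such patients therefore meet the MLFS blast and disease criteria. Because 9.1.2.1 and 9.6.2 are cumulative, counting by criteria met would capture them. Against this, 12.1 gives CRi/CRh and MLFS separate rows, and its stable-disease row names CRi and MLFS separately. That is not an exclusivity rule, but no nesting rule is given either.

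What stands is that the inversion is conditional. It needs exclusive categories, which the plan does not state, and more CRi and CRh than MLFS and PR. The counts above are invented to show scale. ORR has no hypothesis test or decision rule attached. The open DOR set comes from 9.4.3 leaving response undefined, not from the 9.4.2 formula itself.

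A reader might also infer that CRh is missing from all four definitions. For 9.1.2.1 and 9.6.2 that is too strong: 12.1 puts CRh in the CRi row, and a CRh patient short of the CR count thresholds also fits the CRi text.

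**Conclusion.** The contradiction is real and should be corrected. Sections 1.2.1 and 9.4.2 give one ORR, 9.1.2.1 and 9.6.2 give another, and no text reconciles them. Under one best-response category per patient, the 9.4.2 formula excludes CRi and CRh patients. In the main illustration it gives 33% instead of 54%, against a composite CR of 44%. If there are no CRi or CRh patients, the formulas agree.

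Three stronger conclusions are not supported. A reader might infer that the primary result is compromised, but the primary endpoint, sample size and Simon boundaries do not use ORR. A reader might infer that ORR will come out below composite CR, but this depends on the counts and on exclusive categories. A reader might infer that ORR is the only endpoint with a stated confidence interval, but 9.4.2 also specifies 95% intervals for the Kaplan-Meier estimates of overall and progression-free survival.

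**What to change.** Put one formula in 1.2.1, 9.1.2.1, 9.4.2 and 9.6.2: ORR = CR + CRi + CRh + MLFS (marrow CR) + PR, each patient counted once by best response within six cycles. In 9.4.3, state that response in the DOR definition means this set. A second DOR analysis in composite-CR responders would be a matter of preference and is not needed to resolve the contradiction.

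The cost is wording in five places. Every component is already defined in section 12.1 and named in 9.1.2.1, so no new data are needed. The change should be made before the responses are analysed.
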